2. INTRODUCTION

2.1. Study rationale

Neisseria meningitidis infections causing invasive meningococcal disease (IMD) are an important public health concern worldwide due to the substantial morbidity and mortality they cause, as well as the transmissibility of these infections. Ninety percent of meningococcal meningitis and septicaemia are caused by only 5 *N. meningitidis* serogroups: A, B, C, W and Y.

GSK has 2 established meningococcal vaccines against serogroups A, C, W, Y and B respectively, the quadrivalent meningococcal ACWY conjugate vaccine (*Menveo*) and the multi-component recombinant meningococcal B vaccine (*Bexsero*). The availability of a pentavalent meningococcal vaccine in a single administration would however reduce the number of injections, allow greater flexibility in dose administration schedules and increase the coverage for meningococcal disease caused by these serogroups worldwide.

Redacted content

The CCI drug component as well as the final pentavalent CCI have undergone pre-clinical testing in mice, rats and rabbits, to assess immunogenicity and breadth of MenB strain coverage, while a GLP toxicology study to assess local tolerability and systemic toxicity has been concluded. Results from the pre-clinical testing and toxicology study were favourable. Please refer to the current Investigator's Brochure (IB) for information regarding the formulation and pre-clinical studies of CCI vaccine.

The early clinical development plan consists of a seamless Phase I/II study. The first-time-in-human (FTIH), Phase I part of this study will be conducted in healthy adults in a dose-escalating fashion with 2 formulations of the investigational CCI referred to hereafter as CCI respectively, and will serve as a safety lead-in to the Phase II study part.

The Phase II part of the study will be conducted in 2 parts: the 'formulation and schedule-finding' part will follow in healthy adolescents and young adults and it is designed to select the vaccine formulation and the schedule to be tested in Phase III. The 'blood sourcing' part will be conducted in healthy adults in order to collect sufficient serum samples for the development of assays to be used in the CCI vaccine clinical development program. Phase II will assess the safety, the effectiveness and the immunogenicity of the above 2 formulations of the investigational CCI

vaccine. *Bexsero* (rMenB+OMV NZ, hereafter referred to as MenB) and *Menveo* (hereafter referred to as MenACWY) will be administered as control vaccines for assessing the response to serogroups B and ACWY, respectively.

2.2. Background

Neisseria meningitidis is a leading cause of bacterial meningitis and sepsis worldwide, capable of causing outbreaks and epidemics of invasive disease. *N. meningitidis* infections causing IMD are an important public health concern worldwide due to the substantial morbidity and mortality they cause, as well as the transmissibility of these infections. In healthy individuals, IMD can rapidly progress to serious clinical disease and may be associated with poor outcomes, including fatality in ~10% of cases. While the greatest IMD burden is in infants, there is a second peak of disease in adolescents and young adults.

IMD occurs when the normally asymptotically carried encapsulated gram-negative bacterium *N. meningitidis* enters the bloodstream, multiplies and causes sepsis. Once the blood-brain barrier is compromised, development of acute bacterial meningitis represents a neurological emergency and necessitates immediate diagnosis and treatment [Heckenberg, 2014].

Ninety percent of meningococcal meningitis and septicaemia are caused by only 5 *N. meningitidis* serogroups: A, B, C, W and Y. The distribution of serogroups varies geographically and over time. While the disease burden of IMD in higher-income regions, such as Europe and Australia, is largely attributable to serogroup B, in the ‘meningitis belt’ of sub-Saharan Africa, IMD is predominantly caused by serogroups A and W. In the United States (US), serogroups B, C and Y account for most IMD.

The best option for the control of meningococcal disease is the use of effective vaccines that would include all 5 of the most common serogroups responsible for invasive disease. With evidence of meningococcal epidemiology changing over time and across geographies [Cohn, 2015; Halperin, 2012; Harrison, 2009], a vaccine with the broadest possible coverage is an important step toward a definitive and global solution for meningococcal disease prevention. Refer to Section 2.1 for details on GSK’ investigational CCI vaccine in development.

GSK’s Meningococcal Groups A, C, Y and W-135 Conjugate Vaccine (*Menveo*) is a meningococcal oligosaccharide diphtheria CRM₁₉₇ conjugate vaccine licensed for active immunisation to prevent IMD caused by *N. meningitidis* serogroups A, C, W, and Y. It contains a nontoxic mutant of diphtheria toxin (*Corynebacterium diphtheriae* Cross Reacting Material-197, CRM₁₉₇) as the carrier protein and has been demonstrated to be highly immunogenic against serogroups A, C, W and Y and is well tolerated in all age groups. It has been licensed in more than 60 countries; many of these countries have also approved its use in children. In the EU, the vaccine is indicated for use in individuals 2 years of age and older, and in the US, in individuals 2 months to 55 years of age.

The Meningococcal Group B Vaccine (*Bexsero*) contains 3 recombinant proteins [factor H binding protein (fHbp), *Neisseria* adhesin A (NadA), and *Neisseria* Heparin Binding Antigen (NHBA)], combined with Outer Membrane Vesicles (OMV) components from

the New Zealand outbreak strain NZ98/254. *Bexsero* is immunogenic against the majority of circulating meningococcal serogroup B strains and has acceptable reactogenicity and safety profiles when administered to individuals across age groups. The vaccine is currently approved in more than 40 countries worldwide. Although the meningococcal group B vaccine was developed for individuals aged 2 months and older, the actual age range for which this recommendation extends varies depending on the approval from different health authorities.

Please refer to the current IB for information regarding pre-clinical studies of CCI vaccine.

2.3. Benefit/Risk assessment

Detailed information about the known and expected benefits and risks and expected adverse events of CCI vaccine can be found in the IB.

Detailed information about the known and expected benefits and risks and expected adverse events of *Bexsero* (MenB) and *Menveo* (MenACWY) vaccine can be found in the Prescribing Information or Summary of Product Characteristics.

As with all injectable vaccines, immediate systemic allergic reactions to vaccination can occur. In order to be able to treat participants with an immediate systemic allergic reaction to vaccination, all participants will need to remain under close observation for at least 30 minutes after each study intervention (as per the phase in which they are participating: Visit V1 and Visit V3 in Phase I, Visit V1, Visit V3[^] and Visit V4 in Phase II Formulation and Schedule-Finding and Visit V1 and Visit V2 in Phase II Sourcing). Refer to Section 6.1.

[^] except for Control group participants who will have a phone call at this time point (TC).

In terms of study procedures, blood sampling is associated with a risk of syncope, dizziness, local reactions and infection after or during venepuncture. For this reason, blood samples in this study will be obtained by a trained professional and medical assistance will be available. The potential risk of feeling faint, experiencing mild local pain, bruising, irritation or redness at the site where blood was taken, is mentioned in the Informed Consent Form.

Benefit considerations include:

- Potential benefit of receiving the licensed *Bexsero* and *Menveo* vaccines to help protect against meningococcal IMDs caused by *N. meningitidis* serogroups A, B, C, W and Y.
- Contributing to the process of developing new vaccines against *N. meningitidis*.
- Medical evaluations/assessments associated with this study (e.g., physical examinations).

Overall Benefit: Risk conclusion

Considering the measures taken to minimise risk to participants participating in this study and since CCI vaccine is based on 2 of GSK's meningococcal vaccines,

Menveo and *Bexsero*, with well-established safety profiles, the potential risks associated with it are justified by the anticipated benefits that may be afforded to participants receiving CCI vaccine.

3. OBJECTIVES AND ENDPOINTS

Table 11 Study objective(s) and endpoints

(Amended 22 March 2022)

Objectives	Endpoints
Phase I – Safety lead-in, Dose escalation	
Primary	
To evaluate the safety and reactogenicity of the 2 formulations (CCI) of the CCI vaccine.	
 The frequencies and percentages of participants with solicited administration site and systemic events during the 7 days (including the day of vaccination) following each vaccination at Day 1 and Day 31 in all groups. The frequencies and percentages of participants with any unsolicited AEs (including all SAEs, AEs leading to withdrawal, and AESIs) during the 30 days (including the day of vaccination) following each vaccination at Day 1 and Day 31 in all groups. The frequencies and percentages of participants with SAEs, AEs leading to withdrawal and AESIs throughout the study period in all groups (Day 1 through Day 211). The frequencies and percentages of participants with haematological and biochemical laboratory abnormalities, and changes from the baseline values, after the first vaccination at Day 8, in all groups.
Phase II – Formulation and Schedule-finding	
Primary	
To demonstrate the superiority of the effectiveness of the CCI vaccine (CCI) when administered at 0,2- or 0,6-months schedule, compared to the MenB vaccine administered at 0,6-months schedule*.	The percentages of samples with bactericidal serum activity using enc-hSBA against a panel of 110 randomly selected endemic US N. meningitidis serogroup B invasive disease strains at 1 month after the last vaccination (Day 211, Month 7) in all groups.
To demonstrate the immunological non-inferiority of the CCI vaccine (CCI) administered at 0,2- or 0,6-months schedule compared to the MenACWY vaccine (single dose)*;†.	
The percentages of participants achieving a 4-fold rise** in hSBA titres against serogroups A, C, W and Y at 1 month after the
 
 last CCI vaccination (Day 211, Month 7) for the ABCWY groups and, MenACWY vaccination (Day 31, Month 1) in the Control group, 
relative to Day 1, Month 0 in C, C and Control groups and relative to 3 months pre-first CCI vaccination (Day 31, Month 1) in C groups.

CONFIDENTIAL

212458 (MENACWY=CCI -001 PRI)

Protocol Amendment 4 Final

Objectives	Endpoints
To evaluate the safety and reactogenicity of the CCI vaccine (CCI), the MenB vaccine and the MenACWY vaccine.	
• The frequencies and percentages of participants with solicited administration site and systemic events during the 7 days (including the day of vaccination) following each vaccination at:
• Day 1, Day 121 and Day 181 in the C groups, and• Day 1 and Day 181 in the Control group.• The frequencies and percentages of participants with any unsolicited AEs (including all SAEs, AEs leading to withdrawal, and AESIs) during the 30 days (including the day of vaccination) following each vaccination at:
• Day 1, Day 121 and Day 181 in the C groups, and• Day 1 and Day 181 in the Control group.• The frequencies and percentages of participants with SAEs, AEs leading to withdrawal and AESIs throughout the study period in all groups (Day 1 through Day 541).
Phase II –Sourcing	
Primary	
To evaluate the safety and reactogenicity of the 2 formulations (CCI) of the CCI vaccine.	
• The frequencies and percentages of participants with solicited administration site and systemic events during the 7 days (including the day of vaccination) following each vaccination at:
• Day 1 and Day 31 in C groups,• at Day 1 and Day 61 in C groups, and• at Day 1 and Day 181 in C groups.• The frequencies and percentages of participants with any unsolicited AEs (including all SAEs, AEs leading to withdrawal, and AESIs) during the 30 days (including the day of vaccination) following each vaccination at:
• Day 1 and Day 31 C groups,• at Day 1 and Day 61 in C groups, and• at Day 1 and Day 181 in C groups.• The frequencies and percentages of participants with SAEs, AEs leading to withdrawal and AESIs throughout the study period:
• Day 1 through Day 211 in C and

CONFIDENTIAL

212458 (MENACWY=CCI -001 PRI)

Protocol Amendment 4 Final

Objectives	Endpoints
	
CCI groups,
 
 • Day 1 through Day 241 in CCI groups, and • Day 1 through Day 361 in CCI groups).
Phase II – Formulation and Schedule-finding	
Secondary	
To describe the distribution of participants by percentages of serogroup B invasive disease strains killed using enc-hSBA at 1 month after the last vaccination of the CCI vaccine (CCI) administered at 0,2 and 0,6-months schedule and of the MenB vaccine administered at 0,6-months schedule.	The percentages of serogroup B invasive disease strains killed using enc-hSBA in each participant sample at 1 month after the last vaccination (Day 211, Month 7) in all groups.
To assess the immune response to the CCI vaccine (CCI) administered at 0,2 and 0,6-months schedule and to the MenB vaccine administered at 0,6-months schedule against serogroup B indicator strains.	
 • The percentages of participants with hSBA titres \geqLLOQ for each and all serogroup B indicator strains at: 
 ○ Day 1, Month 0 in CCI and Control groups, ○ 3 months pre-first CCI vaccination (Day 31, Month 1) in CCI groups and, ○ 1 month after the last vaccination (Day 211, Month 7) for all study groups. • The percentages of participants with 4-fold rise in hSBA titres** at 1 month after the last vaccination for all study groups (Day 211, Month 7), relative to: 
 ○ Day 1, Month 0 for CCI and Control groups and, ○ 3 months pre-first CCI vaccination (Day 31, Month 1) for CCI groups. • hSBA GMTs against serogroup B indicator strains at: 
 ○ Day 1, Month 0 in CCI and Control groups, ○ 3 months pre-first CCI vaccination (Day 31, Month 1) in CCI groups and, ○ 1 month after the last vaccination (Day 211, Month 7) for all study groups. • hSBA GMRs against serogroup B indicator strains at 1 month after the last vaccination (Day 211, Month 7) for all study groups relative to: 
 ○ Day 1, Month 0 for CCI and Control groups and ○ 3 months pre-first CCI vaccination (Day 31, Month 1) for CCI groups.
To assess the immune response to the CCI vaccine (CCI) administered at 0,2 and 0,6-months schedule and to the MenACWY vaccine (single dose) against serogroups A, C, W and Y.	
 • The percentages of participants with hSBA titres \geqLLOQ for serogroups A, C, W and Y at: 
 ○ Day 1, Month 0 in CCI and Control groups,

CONFIDENTIAL

212458 (MENACWY=CCI -001 PRI)

Protocol Amendment 4 Final

Objectives	Endpoints
	
 ○ 3 months pre-first CCI vaccination (Day 31, Month 1) in C groups, ○ 1 month after the first CCI vaccination (Day 31, Month 1) in the C groups, ○ 1 month after the last CCI vaccination (Day 211, Month 7) for all ABCWY groups and, ○ 1 month after the MenACWY vaccination in the Control group (Day 31, Month 1). ● The percentages of participants with 4-fold rise in hSBA titres** for serogroups A, C, W and Y at 1 month after the first CCI vaccination (Day 31, Month 1) relative to Day 1, Month 0 for C groups. ● hSBA GMTs against serogroups A, C, W and Y at: 
 ○ Day 1, Month 0 in C and Control group, ○ 3 months pre-first CCI vaccination (Day 31, Month 1) in C groups, ○ 1 month after the first CCI vaccination (Day 31, Month 1) in the C groups, ○ 1 month after the last CCI vaccination (Day 211, Month 7) for all ABCWY groups and, ○ 1 month after the MenACWY vaccination in the Control group (Day 31, Month 1). ● hSBA GMRs against serogroups A, C, W and Y at 1 month after: 
 ○ the first CCI vaccination (Day 31, Month 1) in the C groups, ○ the last CCI vaccination (Day 211, Month 7) for all ABCWY groups and ○ the MenACWY vaccination in the Control group (Day 31, Month 1), relative to Day 1, Month 0 for C and Control groups and 3 months pre-first CCI vaccination (Day 31, Month 1) for C groups. ● The total IgG as measured by ELISA GMCs against serogroups A, C, W and Y at: 
 ○ Day 1, Month 0 in C and Control groups, ○ 3 months pre-first CCI vaccination (Day 31, Month 1) in C groups, ○ 1 month after the first CCI vaccination in the C groups and after the MenACWY vaccination in the Control group (Day 31, Month 1) and,

CONFIDENTIAL

[figure not shown]
212458 (MENACWY=CCI -001 PRI)

Protocol Amendment 4 Final

Objectives	Endpoints
	
○ 1 month after the last CCI vaccination (Day 211, Month 7) for all ABCWY groups.

Phase II (Formulation and Schedule-finding)**Tertiary objectives**

CCI

CONFIDENTIAL

212458 (MENACWY=CCI -001 PRI)

Protocol Amendment 4 Final

Objectives	Endpoints
CCI	

Abbreviations: AE, Adverse event; SAE, Serious adverse event; AESI, Adverse event of special interest; ELISA, enzyme-linked immunosorbent assay; GMC, geometric mean concentrations; enc-hSBA, endogenous complement human serum bactericidal assay; GMT, geometric mean titre; GMR, geometric mean ratio; hSBA, human serum bactericidal assay; LOD, limit of detection; LLOQ, lower limit of quantitation.

Note 1: MenB immune response will be assessed against *N. meningitidis* serogroup B indicator strains CCI

Note 2: Evaluation of the tertiary objectives may or not be performed. If the tertiary objectives are evaluated, it may be assessed in a subset of participants using remaining serum after the primary and secondary analyses have been completed; no additional blood samples will be collected from participants.

*All statistical criterion linked to evaluation of the objectives can be found in Section 9.4.

**For the serogroup A C, W, Y and serogroup B evaluations, the 4-fold rise (for serogroup B - per each indicator strain) is defined as:

- a post-vaccination hSBA titre ≥ 16 for participants with a pre-vaccination hSBA titre < 4 ,
- a post-vaccination hSBA titre ≥ 4 times the LLOQ for participants with a pre-vaccination hSBA titre $\geq \text{LOD}$ but $< \text{LLOQ}$, and
- a post-vaccination hSBA titre ≥ 4 times the pre-vaccination hSBA titre for participants with a pre-vaccination hSBA titre $\geq \text{LLOQ}$

[†]The primary objective of immunological NI of the [REDACTED] vaccine to MenACWY will be evaluated only in participants without a previous MenACWY vaccination (unprimed). All other primary and secondary objectives will be evaluated in participants with and without previous MenACWY vaccination (primed/unprimed).

CCII

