Note: All procedures to be performed prior to study intervention administration (as applicable). The study timepoints are the same for all groups, irrespective of the staggered enrolment (See Section 8.2.2.1)

* Diagnosis of COVID-19 should be made in accordance with the World Health Organization case definitions. Cases should be reported as AEs or SAEs (refer to Section 10.3 for the definitions), and routine procedures for recording, evaluation, follow-up, and reporting of AEs, and SAEs should be followed in accordance with the protocol-defined time periods (refer to Table 35). In addition, separate COVID-19 specific eCRF form(s) should be completed.

** The phone call at Day 8 is only for the first 45 participants (15 participants in [REDACTED], 5 participants in [REDACTED], 15 participants in [REDACTED], 5 participants in [REDACTED]

[REDACTED] and 5 participants in the Control groups). Refer to Section 4.1.2.1 and Figure 2 for details.

† Visit V3 (at Day 121) is only applicable for [REDACTED] groups

†† TC (at Day 121) is only applicable for the Control group

‡ Not applicable for Control group

Note 1: If local regulations allow and quality of study procedures is maintained, participant(s) can be offered remote visits (e.g. home visits) for the collection of biological samples and/or study intervention administration (except for Visit V1 which will always be a clinic visit). These remote visits must be performed by qualified study staff/healthcare professionals (HCPs). Details of how these visits will be conducted are outlined in the study procedure manual (SPM). Refer to Section 8 (decentralised study procedures) for details

Note 2: Refer to Section 8 for information on study procedures during special circumstances

Table 4 Intervals between study visits/contacts –Phase II (Formulation and schedule-finding)

Interval	Planned visit interval	Allowed interval range
Visit V1 → Telephone contact T1*	7 days	6 to 8 days (-1 to +1 days)
Visit V1 → Visit V2	30 days	25 to 44 days (-5 to +14 days)
Visit V1 → Telephone contact T2	90 days	83 to 104 days (-7 to +14 days)
Visit V2 → Visit V3/TC**	90 days	85 to 104 days (-5 to +14 days)
Visit V3/TC** → Visit V4	60 days	55 to 74 days (-5 to +14 days)
Visit V4 → Visit V5	30 days	25 to 44 days (-5 to +14 days)
Visit V4 → Telephone contact T3	90 days	83 to 104 days (-7 to +14 days)
Visit V4 → Telephone contact T4	180 days	173 to 194 days (-7 to +14 days)

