4.1.2.1. Phase II: Formulation and Schedule-finding

Phase II (Formulation and Schedule-finding) will include 5 study groups, with a staggered enrolment (45 participants for safety lead-in and 955 participants thereafter) of a total of 1000 participants ([Figure 2](#)):

- **CCI** Participants will receive 2 vaccinations of the **CCI** vaccine in a (0,6-months) schedule.
- **CCI**: Participants will receive 2 vaccinations of the **CCI** vaccine in a (0,2-months) schedule.
- **CCI** Participants will receive 2 vaccinations of the **CCI** vaccine in a (0,6-months) schedule.
- **CCI**: Participants will receive 2 vaccinations of the **CCI** vaccine in a (0,2-months) schedule.

[figure not shown]
The above 4 groups will also receive 1 injection of placebo, according to the schedule described in [Figure 2](#).

- **Control:** Participants will receive 2 vaccinations of MenB vaccine (*Bexsero*) in a (0,6-months) schedule and a single vaccination of MenACWY vaccine (*Menveo*).

For more detailed information on study groups and treatments administered, refer to [Table 13](#) and [Table 16](#).

The schedule of activities in Phase II (Formulation and Schedule-finding) of the study is described in [Table 3](#).

Figure 2 Study design overview – Phase II (Formulation and Schedule-finding)

CONFIDENTIAL

212458 (MENACWY=CCI -001 PRI)
Protocol Amendment 4 Final

Abbreviation: N, number of participants; V, clinic visit; D, day; TC, Telephone contact for Control group only; iSRC, internal safety review committee; PC, phone contact; BS, blood sample.

[^] The phone call at Day 8 is only for the first 45 participants (15 participants in CCI [REDACTED], 5 participants in CCI [REDACTED] 15 participants in CCI [REDACTED] 5 participants in CCI [REDACTED] and 5 participants in the Control groups).

* The outcome of the iSRC will impact the next study intervention at Month 4. The Month 1 blood sampling will proceed as planned.

Note 1: Blood draw at Visit 6 Month 18 will be used only for assessment of tertiary objectives.

Note 2: This figure represents the main aspects of the study design. Refer to [Table 3](#), Schedule of activities, for details on all visits and contacts

Note 3: The Phase II (Formulation and Schedule-finding) is partially blinded. Study conduct and data collection in groups C [REDACTED] [REDACTED] will be observer-blind while in group Control it will be open-label.

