7. DISCONTINUATION OF STUDY INTERVENTION AND PARTICIPANT DISCONTINUATION/WITHDRAWAL

7.1. Discontinuation of study intervention

‘Discontinuation’ of study intervention refers to any participant who has not received all planned doses of study intervention. A participant who discontinued study intervention may continue other study procedures (e.g. safety or immunogenicity), planned in the study protocol at the discretion of the investigator.

The primary reason for premature discontinuation of the study intervention will be documented on the eCRF as follows:

- Adverse event requiring expedited reporting to GSK
- Unsolicited non-serious adverse event
- Solicited adverse event
- Not willing to be vaccinated
- Other (specify).

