Note: the total number of participants (healthy adults) planned to be enrolled in the Phase I and Phase II (Sourcing) is required in order to collect sufficient serum samples for the development of assays to be used in the CCI vaccine clinical development program. All participants will be followed for safety up to 6 months after the last vaccination.

Phase II (formulation and schedule-finding): In order to provide the necessary serum volume for the bactericidal assays (enc-hSBA and/ or hSBA), an overall blood volume of approximately 90mL, per participant, will be collected over the course of the Phase II step of the study. Please refer to [Table 27](#) for details.

Table 27 Blood samples at Phase II (Formulation and schedule-finding)

Sample type	Quantity	Unit	Timepoint	Subset name/ Group	Day
Blood	Approximately 15	mL	Visit V1 (*)	All participants	Day 1
Blood	Approximately 15	mL	Visit V2 (**)	All participants	Day 31
Blood	Approximately 30	mL	Visit V5 (CCI)	All participants	Day 211
Blood	Approximately 30	mL	Visit V6 (^)	All participants	Day 541

* Pre-vaccination (Pre-Vacc) for C and Control groups

** Pre-vacc timepoint for C groups. For rest of the groups, C and Control, this is post-vaccination (post-Vacc 1) timepoint

^ Blood sample will be used only for assessment of tertiary objectives

Note: in case of local regulations limiting the amount of blood to be taken in the younger population (e.g 10-12 years of age and/or at the lower bound of the percentile of the growth chart), a reduced amount of blood volume could be drawn at Phase II, Visit 5 and Visit 6. In this population every effort must be done to collect at least 25mL of blood volume, samples will be analysed according to priority ranking provided in [Table 29](#) and [Table 30](#).

Refer to [Table 3](#) (SoA for Phase II, Formulation and Schedule-finding) for details of visits.

Insufficient blood volume may lead to test cancellation and jeopardise the statistical power. Hence, every effort must be done to collect blood volume as per protocol requirements.

Note 1: Blood samples are taken from all participants in Phase I and II irrespective of the testing status to maintain the blind of the study. Refer to Section [8.1](#) for details on how the unused/ left-over samples will be used.

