10.1.3.11. Onset day

The onset day for an event (e.g., AE, concomitant medication/vaccination) is the number of days between the last study dose and the start date of the event. This is 1 for an event occurring on the same day as a study dose (and reported as starting after study dose).

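### Is the Day 1 to Day 541 safety endpoint flawed because the 0,2-month groups receive only placebo until Day 121?

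*Protocol*

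**What the plan says.** Protocol Section 3 (Table 11) and SAP Section 2 define the long-term safety endpoint in the same words: "participants with SAEs, AEs leading to withdrawal and AESIs throughout the study period in all groups (Day 1 through Day 541"). No sub-period is given. The objective it serves names the ABCWY vaccine, the MenB vaccine and the MenACWY vaccine.

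The same objective has a companion endpoint, which counts "any unsolicited AEs (including all SAEs, AEs leading to withdrawal, and AESIs) during the 30 days (including the day of vaccination) following each vaccination". In the ABCWY groups the injections are on Days 1, 121 and 181.

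Protocol Section 4.1.2.1 gives each ABCWY group two vaccine doses and one saline injection: "The above 4 groups will also receive 1 injection of placebo". Figure 2, which shows the order, is not reproduced, but the order can be recovered. For some groups Table 11 measures the 4-fold rise "relative to 3 months pre-first CCI vaccination (Day 31, Month 1"), and the Table 27 footnote calls Day 31 a "Pre-vacc timepoint for C groups. For rest of the groups, C and Control, this is post-vaccination (post-Vacc 1) timepoint" (CCI and C are redaction marks). Two doses 2 months apart, with the first about 3 months after Day 31, fit only Days 121 and 181. The 0,2-month groups therefore receive saline on Day 1.

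**The concern.** The primary safety endpoint appears to mix two exposures. For their first four months the 0,2-month groups have had saline only, yet an SAE or AESI in that time is counted under the same group label as one that follows the vaccine. The plan handles this for immunogenicity, where the baseline of these groups moves to Day 31, but makes no matching adjustment in the safety endpoint. The 30-day endpoint isolates only the first 30 days after the saline injection.

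Protocol Section 7.1 adds to the worry: "A participant who discontinued study intervention may continue other study procedures (e.g. safety or immunogenicity"). Someone who received only saline could thus be followed beyond Day 121 within an ABCWY group.

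If events before vaccination were read as vaccine events, or if placebo time diluted a vaccine effect in two of the four ABCWY groups, the safety profiles of the two schedules could be misread. This part of the trial exists to choose formulation and schedule.

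**Working it through.** **Calendar (Protocol Table 4, planned intervals).** V1 to V2 is 30 days, V2 to V3 is 90, V3 to V4 is 60 and V4 to V6 is 360.

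- Total: 30 + 90 + 60 + 360 = 540 elapsed days, so V6 is Day 541. This reproduces the plan's end day.
- Before first ABCWY dose in the 0,2-month groups: 30 + 90 = 120 days, and 120/540 = 22.2%.
- Within visit windows, V1 to V2 may be 25 to 44 days and V2 to V3 "85 to 104 days (-5 to +14 days"). The period is then 110 to 148 days. Lowest share: 110/(110 + 74 + 374) = 110/558 = 19.7%. Highest: 148/(148 + 55 + 353) = 148/556 = 26.6%.

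**What the 30-day endpoint separates.** It takes 30 of the 120 days and leaves 90. This gap is not peculiar to the placebo period. With three injections, every ABCWY group has 3 x 30 = 90 days inside the windows and 540 - 90 = 450 outside. Control, with injections on Days 1 and 181 only, has 60 inside and 480 outside. Days 31 to 120 are outside for all five groups. That is the normal shape of a short-window endpoint paired with a whole-study endpoint.

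**Is the group comparison unequal?** Under the plan's endpoint every group has 540 planned days. An imbalance of 420 against 540 days appears only if the clock restarts at first ABCWY dose. With no vaccine effect and an assumed 2 SAEs per 100 person-years, such a restart gives 1 - exp(-0.02 x 420/365.25) = 2.3% against 1 - exp(-0.02 x 540/365.25) = 2.9%. That difference comes from the alternative analysis and does not exist in the planned one.

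**Size.** The documents give no SAE rate, so 1 to 3 per 100 person-years is an assumption. The lead-in lists 15, 5, 15, 5 and 5 participants in the order in which the groups are listed, followed by 191 per group. The 0,2-month groups are thus inferred to have 5 + 191 = 196 participants each.

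| Days | Formula | 1 per 100 | 2 per 100 | 3 per 100 |
|---|---|---|---|---|
| 120 (before ABCWY) | 196 x rate x 120/365.25 | 0.64 | 1.29 | 1.93 |
| 90 (of these, after Day 30) | 196 x rate x 90/365.25 | 0.48 | 0.97 | 1.45 |

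With 206 per group, the first row would be 0.68 to 2.03.

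**Where a split would be stated.** An endpoint table says what is counted. Denominators, sub-periods and displays belong in the analysis sections: Protocol 9.4.2, SAP Section 4 (analysis sets) and SAP 5.3 (primary endpoints). Their content is redacted. The SAP document history shows that these sections hold more than the endpoint table does. Amendment 4 added a classification of each AESI as new onset or exacerbation to every safety subsection, and the endpoint wording does not mention it.

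**Can events before ABCWY be identified?** Yes. SAP 10.1.3.11 defines onset day, which "is the number of days between the last study dose and the start date of the event", and the date of each dose is recorded (Protocol 6.4). Protocol 10.3.9.2 also requires a causality assessment for every unsolicited AE and SAE.

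**The case for a change.** The strongest case for the concern is dilution. Suppose the background rate is constant and the vaccine raises it by a sustained ratio R after first dose. The whole-period ratio in the 0,2-month groups is then (120 + 420R)/540. R = 2 gives 960/540 = 1.78, and R from 1.5 to 3 gives 1.39 to 2.56. The 0,6-month groups would show R in full, so equal vaccine risk could look like a schedule difference. The arithmetic stands. It requires an effect lasting the whole follow-up, and a short-lived risk would be distorted less. It also bears on how a descriptive table is read, and leaves the comparison of randomised groups valid.

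A second argument is that SAP 5.3.2, 9.1 and 9.2 read NA, so no extra rule may exist. This is weak evidence. Those entries cover additions to the planned analysis and study-specific derivations, while the planned analysis itself is what is redacted.

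Third, the onset-day rule as visible does not distinguish saline from vaccine, and observer-blind investigators judge causality without knowing which was given. Both are true, but the dose records identify the product once the data are unblinded.

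The Section 7.1 point carries little weight. Continuation is at the investigator's discretion, no number is given, and the handling of such participants depends on the redacted safety set.

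**Conclusion.** The concern does not hold. The facts behind it are right: saline on Day 1, first ABCWY dose on Day 121, 22% of planned time before exposure, and no split in the visible endpoint wording. They do not make the endpoint wrong. Followed as written, it gives a valid comparison by randomised group over equal planned follow-up, for an objective that includes the control vaccines. The per-injection endpoint separates events soon after saline from those soon after vaccine. Because the sections that would contain a split are redacted, its absence cannot be held against the plan.

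The amount in question is about 0.6 to 1.9 SAEs per 0,2-month group at the assumed rates. AESIs and AEs leading to withdrawal are not sized, because the documents give no rates for them. The hypotheses in Protocol 9.1.2 concern only effectiveness and immunogenicity, so no visible test, power figure or success criterion changes. A table split at first ABCWY dose, with incidence per person-time, would be a useful descriptive supplement. Choosing to add it is a matter of preference. This conclusion rests on the inferred saline position, which is firm, and makes no assumption about what the redacted text contains.
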